10.3.2.1 Analysis of Quality of Life Endpoints

IGART

The number and percentage of subjects with each response for the IGART (none, poor, fair, good or excellent) as well as for the cumulative categories poor or better, fair or better, good or better will be presented by visit.

For the percentage of cumulative responses, a two-sided 95% CI will be presented. The Friedman test will be used to compare the percentage of subjects with good or excellent responses between study Visit Month 12, study Visit Month 24 and study Visit Month 36. The test will be exploratory with an alpha of 5%. The shift tables for SGART (described in [Section 10.2.1.5](#)) will be repeated for IGART.

WPAI:GH, TQSM and AE-QoL

Unlike for the other analyses in this SAP, the analyses described in this section will be only performed separately for treatment-naïve subjects and non-treatment-naïve subjects (see [Section 8.3.2](#)), without pooling them together.

For the WPAI:GH, TSQM, and AE-QoL, total and domain scores will be presented descriptively by study visit as well as the individual changes in scores between the baseline visit and subsequent visits.

Two-sided 95% CIs for the differences will be presented.

The proportion of subjects achieving a minimal clinically important difference (MCID) will be calculated for Baseline and Visit Month 24 and Visit Month 30 for the total and domain scores.

The MCID for the AE-QoL is defined as -6. For the WPAI:GH and the TSQM, the MCID will be estimated using the half SD approach which has been shown to approximate the threshold of discrimination for a clinically meaningful change. The SD at Baseline will be used to derive the MCID.

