8.6.3.3 Treatment Period: Months 3, 18, and 30 ± 4 days

The following procedures / assessments will be conducted at the Months 3, 18, and 30 site visits:

- Perform physical examination.
- Record vital signs, including body weight.
- TSQM II (subjects ≥ 18 years) (at Months 3 and 18 only).
- AE-QoL (subjects ≥ 18 years) (at Months 3 and 18 only).
- WPAI:GH (subjects ≥ 16 years) (at Months 3 and 18 only).
- Urine collection for urinalysis (at Months 18 and 30 only).
- Collection of blood to assess:
 - Hematology.
 - Biochemistry.
 - Coagulation.
 - Retention sample for HAE biomarkers (adults only).
 - PK / PD.
- Collect urine for pregnancy test (for women of childbearing potential).
- Review eDiary data and assess / document HAE attacks.
- Confirm access to on-demand HAE medication.
- IRT CSL312 kit assignment.
- CSL312 accountability.

- At Month 3 only, subcutaneous administration of CSL312 dose by investigator or delegate or by subject under the supervision of the investigator or delegate (after completion of physical examination and vital signs). Subjects will complete the Medication Dosing Diary on the eDiary after dosing at the site is complete.
- Record concomitant medications and therapies (type, dose, route, date, and time).
- Record AEs.

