8.6.3.4 Treatment Period: Months 6, 12, and 24 ± 4 days

The following procedures / assessments will be conducted at the Months 6, 12, and 24 site visits:

- Perform physical examination.
- Record vital signs, including body weight.
- SGART / IGART (all ages) (at Months 12 and 24 only).
- TSQM II (subjects ≥ 18 years).
- AE-QoL (subjects ≥ 18 years).
- WPAI:GH (subjects ≥ 16 years).
- Urine collection for urinalysis.
- Collection of blood to assess:
 - Hematology.
 - Biochemistry.
 - Coagulation.
 - Retention sample for HAE biomarkers (adults only).
 - PK / PD.
 - Immunogenicity
- Collect urine for pregnancy test (for women of childbearing potential).
- Review eDiary data and assess / document HAE attacks.
- Confirm access to on-demand HAE medication.

- IRT CSL312 kit assignment.
- CSL312 accountability.
- Record concomitant medications and therapies (type, dose, route, date, and time).
- Record AEs.

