8.6.3.5 Treatment Period: Month 9 ± 4 days

The following procedures / assessments will be conducted at the Month 9 site visit:

- Perform physical examination.
- Record vital signs, including body weight.
- TSQM II (subjects ≥ 18 years).
- AE-QoL (subjects ≥ 18 years).
- WPAI:GH (subjects ≥ 16 years).
- Collection of blood to assess:
 - Retention sample for HAE biomarkers (adults only).
 - PK / PD.
- Collect urine for pregnancy test (for women of childbearing potential).
- Review eDiary data and assess / document HAE attacks.
- Confirm access to on-demand HAE medication.
- IRT CSL312 kit assignment.
- CSL312 accountability.
- Record concomitant medications and therapies (type, dose, route, date, and time).
- Record AEs.

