8.6.4.2 Treatment Period: Month 3 ± 4 Days

The following procedures / assessments will be conducted at Month 3:

- Perform physical examination.
- Record vital signs, including body weight.
- Collection of blood to assess:
 - Retention sample for HAE biomarkers (adults only).
 - PK / PD.
- Collect urine for pregnancy test (for women of childbearing potential).
- Review eDiary data and assess / document HAE attacks.
- Confirm access to on-demand HAE medication.
- IRT CSL312 kit assignment.
- CSL312 accountability.
- Record concomitant medications and therapies (type, dose, route, date, and time).
- Record AEs.

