8.6.4.3 Treatment Period: Months 6, 18, and 30 ± 4 Days

The following procedures / assessments will be conducted at Months 6, 18, and 30:

- Perform physical examination.
- Record vital signs, including body weight.
- TSQM II (subjects ≥ 18 years) (at Months 6 and 18 only).
- AE-QoL (subjects ≥ 18 years) (at Months 6 and 18 only).
- WPAI:GH (subjects ≥ 16 years) (at Months 6 and 18 only).
- Urine collection for urinalysis.
- Collection of blood to assess:
 - Hematology.
 - Biochemistry.
 - Coagulation.
 - Retention sample for HAE biomarkers (adults only).
 - PK / PD.
 - Immunogenicity (at Month 6 only).
- Collect urine for pregnancy test (for women of childbearing potential).
- Review eDiary data and assess / document HAE attacks.
- Confirm access to on-demand HAE medication.
- IRT CSL312 kit assignment.
- CSL312 accountability.
- Record concomitant medications and therapies (type, dose, route, date, and time).
- Record AEs.

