8.3.2 Treatment-naïve and Non-treatment-naïve Subpopulations

The following two subpopulations will be defined:

- Treatment-naïve: Subjects who did not receive CSL312 before the start of this study, including CSL312-naïve subjects and rollover subjects who received only placebo in the CSL312_3001 study. There are no placebo subjects from CSL312_2001, so no subject rolling over from that study will be included in this subpopulation.
- Non-treatment-naïve: Rollover subjects who received CSL312 previously (ie, non-placebo subjects from CSL312_3001 and subjects from CSL312_2001).

In specific tables, the treatment-naïve subjects may be further differentiated into subjects with loading dose (newly enrolled for CSL312_3002) or without loading dose (rollover subjects previously receiving placebo).

The subgroup analyses that will be conducted for those subpopulations are presented in [Table 5](#) (see [Section 17](#)).

The main tables for QoL questionnaires WPAI:GH, TSQM II and AE-QoL will be presented stratified by treatment-naïve and non-treatment-naïve subjects (see [Sections 10.3.2.1](#) and [12](#) for further details). The time-to-event analysis (see [Section 10.3.1](#)) will be performed only for treatment-naïve subjects, with a further break-down of whether they received a loading dose. For these endpoints, this is considered the main analysis, not an additional subgroup analysis.

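### In the non-treatment-naïve quality-of-life tables, Months 3 and 9 can hold only CSL312_3001 rollovers, so differences between visits partly reflect who was measured (minor)

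*SAP*

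**What the plan says.** SAP 10.3.2.1 reports these three questionnaires in two strata and does not pool them: the analyses "will be only performed separately for treatment-naïve subjects and non-treatment-naïve subjects". Within each stratum, "total and domain scores will be presented descriptively by study visit", together with individual changes from baseline. SAP 8.3.2 defines the non-treatment-naïve stratum as "Rollover subjects who received CSL312 previously (ie, non-placebo subjects from CSL312_3001 and subjects from CSL312_2001".

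The protocol gives those two sources different schedules.

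- CSL312_3001 rollovers (and CSL312-naïve subjects): Protocol 8.6.3.3 has "AE-QoL (subjects ≥ 18 years) (at Months 3 and 18 only". Section 8.6.3.4 ("The following procedures / assessments will be conducted at the Months 6, 12, and 24 site visits") and section 8.6.3.5 ("The following procedures / assessments will be conducted at the Month 9 site visit") both list all three questionnaires.
- CSL312_2001 rollovers: section 8.6.4.2 ("The following procedures / assessments will be conducted at Month 3") lists no questionnaire. Section 8.6.4.3 has "AE-QoL (subjects ≥ 18 years) (at Months 6 and 18 only", and section 8.6.4.4 lists the questionnaires at Months 12 and 24. There is no Month 9 visit in this schedule.

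The Schedule of Assessments tables agree with this text for both groups.

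**The concern.** A reader of the by-visit table will follow the non-treatment-naïve column from Day 1 through Months 3, 6, 9 and 12 as one group over time. It is not one group: part of it leaves at Month 3, returns at Month 6, leaves at Month 9 and returns at Month 12, by design and not through dropout. If the two cohorts score differently, the column will rise and fall with no change in any subject.

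Nothing in the current SAP repairs this. Data are summarised by nominal visit without windows, and unscheduled records stay out of summaries (SAP 8.2.5). Nothing is imputed (SAP 10.3). No repeated-measures model is planned for these endpoints.

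A cohort difference is plausible. CSL312_2001 rollovers enter at Day 399 of a dose-ranging study (Protocol 1.2.3.2 and 8.6.4.1). CSL312_3001 rollovers enter at Day 182 of a study of 200 mg once monthly (Protocol 1.2.3.2 and 8.6.3.1). What is at stake is the reading of a quality-of-life trend over the first year in previously treated subjects.

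**Working it through.** The plan states no figure on this point, so there is none to reproduce.

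**Step 1: compare the schedules** (original protocol).

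| Visit | CSL312_3001 rollovers | CSL312_2001 rollovers |
|---|---|---|
| Day 1 | yes | yes |
| Month 3 | yes | visit, no questionnaire |
| Month 6 | yes | yes |
| Month 9 | yes | no visit |
| Month 12 | yes | yes |
| Month 18 | yes | yes |
| Month 24 | yes | yes |

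Months 3 and 9 belong to CSL312_3001 alone, and no visit belongs to CSL312_2001 alone. Under Amendment 1, which a subject can enter from Month 12, the questionnaires are completed for the last time at the consent visit, or at the last scheduled visit before an unscheduled consent visit (Schedule of Assessments under Amendment 1, footnote G; Protocol 8.6.6.1). Who contributes at Months 18 and 24 therefore also depends on the timing of consent. The visits that both groups share without that complication are Day 1 and Months 6 and 12.

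**Step 2: formula.** Let w be the CSL312_2001 share of the stratum and D the difference between the two cohort means.

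- Pooled mean at a shared visit = (1 − w) × mean(3001) + w × mean(2001)
- Mean at Month 3 or 9 = mean(3001)
- Shift due to composition alone = w × D

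**Step 3: inputs.** Protocol 1.2.3.2 gives 36 completers of CSL312_2001 and 64 subjects randomised in CSL312_3001. It does not give the CSL312_3001 arm split or the uptake of rollover from either study. Assumptions: arm split 1:1, 3:2 or 2:1; CSL312_3001 uptake 75-100%; 18 to 36 rollovers from CSL312_2001. For D, the AE-QoL MCID of 6 points in SAP 10.3.2.1 serves only as a yardstick.

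**Step 4: results.**

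- Lowest share: 64 × 2/3 ≈ 43 from CSL312_3001 and 18 from CSL312_2001. w = 18/61 = 0.295; shift = 0.295 × 6 = 1.8 points.
- Highest share: 64 × 0.5 × 0.75 = 24 from CSL312_3001 and 36 from CSL312_2001. w = 36/60 = 0.600; shift = 0.600 × 6 = 3.6 points.
- Full rollover from both studies: w = 36/79 = 0.456 (2:1) to 36/68 = 0.529 (1:1); shift = 2.7 to 3.2 points.
- D needed for a shift as large as the MCID: 6/0.600 = 10 points to 6/0.295 = 20 points.

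**Step 5: illustration.** Take 38 CSL312_3001 subjects constant at 20 and 36 CSL312_2001 subjects constant at 14. The pooled mean is (38 × 20 + 36 × 14)/74 = 17.1. The column reads 17.1, 20.0, 17.1, 20.0, 17.1 at Day 1 and Months 3, 6, 9 and 12, although nobody changed. The mean change from baseline is 0 at every visit, so in this example the artefact sits entirely in the raw scores.

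The age limits (18 for AE-QoL and TSQM II, 16 for WPAI:GH; Protocol 8.2.1) are not in these counts. CSL312_3001 enrolled six adolescents whose arm is not stated; removing any of them would raise w.

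**The case against.** The strongest reply is that the documents show a change in composition but no bias. No section gives a quality-of-life difference between the cohorts. Both baselines are taken in subjects already on CSL312, and Protocol 1.2.3.2 describes the CSL312_2001 effect as sustained through its second treatment period. Change from baseline removes any constant difference in level, so that column is distorted only if the cohorts change by different amounts. All of this stands, and it is why no size can be claimed. It does not rescue the raw by-visit scores, which SAP 10.3.2.1 also presents.

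The second reply is that the tables report the number of observations (SAP 7), so the drop at Months 3 and 9 will be visible. That is true, but the count does not say which cohort is absent, or that the absence is by design.

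Three stronger readings are tempting and are not supported.

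- A reader might infer that the MCID results are distorted too. Those proportions are set for Baseline and Months 24 and 30, so the gap at Months 3 and 9 does not reach them.
- A reader might cite the absence of these questionnaires from SAP Table 5 as proof that no split by parent study is planned. The text before the table says it leaves them out by design, so its silence proves nothing. The word that excludes a further split is the restriction in SAP 10.3.2.1 itself.
- A reader might take Months 18 and 24 as clean common visits because both original schedules include them. Under Amendment 1 they are not.

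**Conclusion.** The point holds as a matter of composition. In the non-treatment-naïve stratum, by-visit results at Months 3 and 9 describe CSL312_3001 rollovers only, and those at Day 1 and Months 6 and 12 describe both sources. Contrasts between these visits cannot be read as change over time alone, least of all in raw scores.

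A reader might go further and infer that the table will show a false saw-tooth of known size. The documents do not support that: the 1.8-3.6 points rest on an assumed share of 30-60% and an assumed 6-point difference, and an artefact as large as the MCID would need a cohort difference of about 10 to 20 points.

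The treatment-naïve stratum is unaffected, because CSL312-naïve subjects and former placebo subjects from CSL312_3001 follow the same schedule. Severity is minor: the endpoints are exploratory, the summaries descriptive, and no confirmatory test depends on them.

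**What to change.** In SAP 10.3.2.1, for the non-treatment-naïve stratum, add by-visit columns for two groups that SAP 8.3.3 already defines: CSL312_3001 rollovers previously on CSL312, and CSL312_2001 rollovers previously on CSL312. Show the combined column only at Day 1 and Months 6 and 12. If it is also shown at Months 18 and 24, add a footnote that composition there depends on when subjects consented to Amendment 1.

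Within each cohort column, the schedule-driven shift at Months 3 and 9 becomes zero; the CSL312_2001 column is simply empty at those visits. This matches the SAP's practice elsewhere: the SGART comparison uses only subjects assessed at both visits (10.2.1.5), and the attack-rate windows use only subjects who cover the whole window (10.2.2).

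The cost is a wording change and extra table columns, with no new data or derivations. The downside is smaller groups per column and so wider intervals. If the columns are not wanted, the least that would help is a footnote saying that Months 3 and 9 include only CSL312_3001 rollovers.

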- G: PRO QoL assessments will be completed for the last time at the visit that the subject consents to Amendment 1 (ie, Month 12, Month 18, Month 24, or Month 30). If consent into Amendment 1 and switching to CSL312 200 mg AI is performed at an unscheduled visit after the Month 12 Visit, the last data for PRO QoL assessments will be from the last visit prior to the unscheduled visit (under the original protocol).
- H: Urine collection for urinalysis will be collected for the last time at the visit that the subject consents to Amendment 1 (ie, Month 12, Month 18, Month 24, or Month 30). If consent into Amendment 1 and switching to CSL312 200 mg AI is performed at an unscheduled visit after the Month 12 Visit, the last data for urinalysis will be from the last visit prior to the unscheduled visit (under the original protocol).
- I: On a visit day, blood draws should be completed on the same day of CSL312 administration.
- J: Per Amendment 1, collection of blood sample for hematology / biochemistry / coagulation analysis will be required every 12 months starting from the Month 12 Visit.
- K: Blood samples for potential future assessment of HAE biomarkers will be obtained for the last time at the visit that the subject consents to Amendment 1 (ie, Month 12, Month 18, Month 24, or Month 30). If consent into Amendment 1 and switching to CSL312 200 mg AI is performed at an unscheduled visit after the Month 12 Visit, the last collection of HAE biomarkers will be from the last visit prior to the unscheduled visit (under the original protocol). These samples will be stored for potential future assessment of HAE biomarkers and will be destroyed within 5 years after completion of the study. These samples will not be collected in adolescents.
- L: The urine test for beta-human chorionic gonadotropin will be performed only for women of childbearing potential. A serum pregnancy test will be performed by the site if urine result is inconclusive. Female subjects of childbearing potential will perform home urine testing on months for which there is no onsite visit.
- M: At the Follow-up Visit (conducted via telephone call), HAE attacks will be reported verbally, as the eDiary is deactivated at the End of Treatment Visit.

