1. Absenteeism: Percent work time missed due to problem: $100 * [Q2 / (Q2 + Q4)]$.
2. Presenteeism: Percent impairment while working due to problem: $100 * [Q5 / 10]$.
1. Work productivity loss: Percent overall work impairment due to problem:
 $100 * \{Q2 / (Q2 + Q4) + (1 - Q2 / (Q2 + Q4)) * (Q5 / 10)\}.$
3. Activity impairment: Percent activity impairment due to problem: $100 * (Q6 / 10).$

Where,

Q2 = hours missed due to health problems,

Q4 = hours actually worked,

Q5 = degree health affected productivity while working,

Q6 = degree health affected regular activities.

Each score is interpreted separately.

AE-QoL

The AE-QoL consists of 17 items and subjects are asked to judge how often they have been restricted in different areas of their daily life because of angioedema and to give more details about their difficulties during the last 4 weeks. The rating for each of the 17 items consists of “Never”, “Rarely”, “Occasionally”, “Often” and “Very Often”. Responses are scored on a scale from 1 to 5, where 1 is “Never” and 5 is “Very Often”.

The items are assigned to four dimensions - Functioning, Fatigue/Mood, Fears/Shame and Nutrition - as follows:

Dimensions	Item
Functioning	1. Impairment of work
	2. Impairment of physical activity
	3. Impairment of spare time activities
	4. Impairment of social relations
Fatigue/Mood	6. Difficulties of falling asleep
	7. Waking up during the night
	8. Feeling tired during the day
	9. Difficulties in concentrating
	10. Feeling downhearted
Fears/Shame	12. Feeling burdened at having swellings
	13. Fear of new suddenly appearing swellings
	14. Fear of increased frequency of swellings
	15. Ashamed to visit public places
	16. Embarrassed by the appearance of swellings

	17. Fear of long term negative drug effects
Nutrition	5. General limitations in foods and eating
	11. Limitations in the selection of food and beverages

It is possible to calculate four individual AE-QoL scores for the four different dimensions or to calculate one AE-QoL total score (Item 1 to Item 17).

The four AE-QoL scores for the four different dimensions as well as the AE-QoL total score are calculated by using the following formula:

$$[(\Sigma \text{ items} - \min \Sigma \text{ items}) / (\max \Sigma \text{ items} - \min \Sigma \text{ items})] \times 100$$

where

$\Sigma \text{ items}$ is the sum of all non-missing item scores within a dimension or all items, respectively,

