$\min \Sigma \text{ items}$ is the sum of the minimum score 1 which is added up as many times as there are non-missing item scores within a dimension or all items, respectively,

$\max \Sigma \text{ items}$ is the sum of the maximum score 5 which is added up as many times as there are non-missing item scores within a dimension or all items, respectively.

For the following example for the dimension “Functioning”:

Item 1: Occasionally (3)

Item 2: Rarely (2)

Item 3: Often (4)

Item 4: Very Often (5)

the AE-QoL score would be calculated by

$$\Sigma \text{ items: } (3+2+4+5) = 14$$

$$\text{min } \Sigma \text{ items: } (1+1+1+1) = 4$$

$$\text{max } \Sigma \text{ items: } (5+5+5+5) = 20$$

resulting in $[(14 - 4) / (20 - 4)] \times 100 = 62.5\%$.

The four AE-QoL scores for the four different dimensions should not be calculated if more than one item is missing in that dimension. The AE-QoL total score should not be calculated if more than 4 items are missing.

The scores are range between 0 and 100 %. The higher the percentage the stronger the impairment the subject has.

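### Quality-of-life MCID proportions are planned at Months 24 and 30, where questionnaire data come from selected subjects, and not at Month 12; the AE-QoL threshold of -6 is a single item-step in two of four domains

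*SAP*

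**What the plan says.** SAP 10.3.2.1 plans by-visit descriptive summaries of scores and changes from baseline, with 95% CIs, for WPAI:GH, TSQM II and AE-QoL. Treatment-naïve and non-treatment-naïve subjects are analysed separately and never pooled. It adds a responder measure: the proportion reaching an MCID "will be calculated for Baseline and Visit Month 24 and Visit Month 30 for the total and domain scores". On the threshold it states: "The MCID for the AE-QoL is defined as -6". WPAI:GH and TSQM II use half the baseline SD instead. No separate AE-QoL domain threshold is given.

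The protocol decides when the questionnaires exist. Protocol 8.6.3.3 (3001 rollovers and CSL312-naïve subjects; Months 3, 18 and 30) lists "AE-QoL (subjects ≥ 18 years) (at Months 3 and 18 only". Protocol 8.6.4.3 (2001 rollovers; Months 6, 18 and 30) lists "AE-QoL (subjects ≥ 18 years) (at Months 6 and 18 only". TSQM II and WPAI:GH carry the same restrictions. Footnote G to the Amendment 1 Schedule of Assessments states: "PRO QoL assessments will be completed for the last time at the visit that the subject consents to Amendment 1". That consent can be given from the Month 12 visit onwards.

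**The concern.** A responder proportion is useful only at a visit where the intended population is measured. If one planned visit is outside the general questionnaire schedule and the other is reached only by those who consented late or not at all, the proportions describe subjects selected by when they switched device. The visit with the fullest coverage would have no responder figure.

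The threshold raises a second problem. A clinically important change should be more than the smallest change the scale can register. Where one category on one item already passes -6, the responder rate for that domain is only the rate of any net improvement, reported under a label that claims more.

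**Working it through.** **Visits.** Collection of AE-QoL, WPAI:GH and TSQM II, read from the three treatment-period schedules and Protocol 8.6.3, 8.6.4 and 8.6.6:

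| Visit | Original protocol: 3001 rollovers and naïve | Original protocol: 2001 rollovers | Amendment 1 |
|---|---|---|---|
| Month 6 | yes | yes | before consent is possible |
| Month 12 | yes | yes | yes |
| Month 18 | yes | yes | only those consenting at Month 18 |
| Month 24 | yes | yes | only those consenting at Month 24 |
| Month 30 | no | no | only those consenting at Month 30 |
| End of Treatment | no | no | no |

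If consent is given at an unscheduled visit after Month 12, footnote G takes the last questionnaire from the preceding scheduled visit. Subjects with at least 12 months in the study who decline the autoinjector receive one more dose and go to End of Treatment, where nothing is collected. Three results follow.

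- Month 30: no subjects under the original schedule; under Amendment 1, Month 30 consenters only.
- Month 24: let f be the share who consented or left before Month 24. Coverage is 1 - f. The documents do not give f, so coverage could lie anywhere from 0 to 100%.
- Month 12: consent cannot come earlier, so every age-eligible subject still on study is scheduled (AE-QoL and TSQM II from 18 years, WPAI:GH from 16).

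**Could subjects have consented before Month 24?** SAP Section 3 dates Amendment 1 to 27 October 2022. Protocol 1.2.3.2 has subjects entering 3001 treatment from April 2021; I assume 1 April. Day 182 of 3001 is Day 1 here (Protocol 8.6.3.1), so the earliest 3001 rollover starts 181 days later, on 29 September 2021. Month 18 (Day 541) then falls on 23 March 2023, 4.8 months after the amendment date. Month 24 (Day 721) falls on 19 September 2023, 10.7 months after. Consent before Month 24 was therefore feasible for 3001 rollovers. How many did so is not stated, nor are site approval dates.

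**Threshold.** Inputs from SAP 10.3.2: items scored 1 to 5; 4 items in Functioning, 5 in Fatigue/Mood, 6 in Fears/Shame, 2 in Nutrition, 17 in the total. Score = 100 × (sum - min) / (max - min).

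The SAP's own example (items 3, 2, 4, 5) is reproduced: 100 × (14 - 4) / (20 - 4) = 62.5.

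For k answered items, max - min = 5k - k = 4k, so one category on one item moves the score by 100/(4k):

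| Score | k | One step | Steps needed for 6 points | Change at that point |
|---|---|---|---|---|
| Functioning | 4 | 6.25 | 1 | 6.25 |
| Fatigue/Mood | 5 | 5.00 | 2 | 10.00 |
| Fears/Shame | 6 | 4.17 | 2 | 8.33 |
| Nutrition | 2 | 12.50 | 1 | 12.50 |
| Total | 17 | 1.47 | 5 | 7.35 |

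On the total, four steps give 5.88, just short. No attainable change equals exactly 6, so the choice between strict and non-strict inequality is immaterial.

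Missing items enlarge the step. The SAP says a domain score "should not be calculated if more than one item is missing in that dimension", so one missing item is allowed. With the same item missing at both visits, the steps become 8.33 (Functioning), 6.25 (Fatigue/Mood), 5.00 (Fears/Shame) and 25.0 (Nutrition). Fatigue/Mood then joins the domains where one step suffices. The total, with the four missing items it allows, has a step of 100/(4 × 13) = 1.92, still well under 6.

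**The case against.** The strongest reply is that little depends on this. AE-QoL, WPAI:GH and TSQM II are exploratory (Protocol 2.3.2). The study tests no confirmatory hypothesis, and the primary endpoint is TEAEs. SGART, the one secondary patient-reported measure, is not affected. Month 12 is not left unanalysed: scores and changes from baseline are summarised at each visit, and only the responder proportion is confined to late visits. SAP Section 7 requires numbers of observations, so a thin visit should show in the output. All of this stands, and it limits the severity.

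Three stronger readings are tempting, and the documents do not support them.

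- A reader might infer that questionnaires are mostly missing at Month 24. It is a scheduled questionnaire visit for every cohort under the original protocol, and the share lost to earlier consent is not given. Nor is Month 30 necessarily empty, since Month 30 consenters contribute.
- A reader might infer that the SAP plans a responder analysis of a change that is zero by definition, because it names Baseline as a visit. The preceding text concerns changes from baseline, so this is probably loose wording that needs only clarifying.
- A reader might infer that -6 fails for AE-QoL domains in general. With complete items it is a single step in two of four domains, and it discriminates on the total.

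**Conclusion.** The concern holds in a limited form. Month 30 is not a general questionnaire visit under either protocol version. Month 24 describes a selected subset of unknown size, divided again because the two treatment-history groups are not pooled. Month 12, where coverage is best, has no MCID proportion. In Functioning and Nutrition the -6 rate equals the rate of any net improvement.

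The visit conclusions rest on the schedules as written. The threshold conclusion rests on the SAP's scoring formula and on reading its single value of -6 as applying to domain scores, which is what the sentence on total and domain scores implies. No primary or secondary conclusion changes. This should be fixed, but it does not threaten the trial's main results.

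**What to change.** In SAP 10.3.2.1:

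- Make Month 12 the main MCID visit and add Month 6, which is also common to all cohorts.
- Show Months 18 and 24 as supportive, with n. Month 18 has the same consent-driven selection as Month 24.
- Delete Month 30, or label it as Month 30 consenters only.
- Reword the Baseline reference as change from Baseline.
- Report the -6 responder proportion for the AE-QoL total only, and leave domains as change from baseline, which is already planned. If a domain threshold is kept, print the one-step size beside it.

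Two alternatives are weaker. Extending the half-SD rule to AE-QoL domains removes the one-step problem only if half the baseline SD exceeds the step: an SD above 12.5 for Functioning and above 25 for Nutrition. The documents give neither SD. Using each subject's last questionnaire visit would mix different follow-up times.

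The cost is SAP wording, a few more descriptive columns, and the loss of a domain-level AE-QoL responder rate. No new data are needed. SAP version 2.0 is dated 2 October 2025, after the September 2025 limit for End of Treatment visits, so the change should be recorded as driven by the visit schedule. If the database is already locked, it belongs in the clinical study report as a deviation, as SAP Section 3 provides.
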